LSLV	Last Subject Last Visit
MedDRA	Medical Dictionary for Regulatory Activities
NA	Not Applicable
PD	Protocol Deviation
PPS	Per-Protocol Set
SAE	Serious adverse event
SAP	Statistical Analysis Plan
SD	Standard Deviation
SDTM	Study Data Tabulation Model
SR	Study Report
TFI	Tables Figures and Listings
TOC	Table of Content

1. DOCUMENT HISTORY

SAP Version	Approval Date	Protocol Version (Date) on which SAP is Based	Change	Rationale
SAP	17 September 2019	Amendment 1: 14 August 2019	Not Applicable	Original version
SAP amendment 1	13 January 2022	Amendment 5: 15 April 2021	
CCI
 
[REDACTED]
 
 • Footnote updated in objective table • Unsolicited and solicited safety set sections added • Title section 4.7.3.1.1 and 4.7.3.1.2 updated • Section 5.1.2 addition of analysis regarding COVID-19 • Section 6.1 change in the testing strategy 	
CCI
 
[REDACTED]
 
 • Clarification that reporting of changes to the NHBA strain during the study will be documented in the clinical study report. • Safety analysis will finally use those sets and not the exposed set • To fit the addition of the two unsolicited and solicited sets • addition of analysis regarding COVID-19 to fit guidelines

CONFIDENTIAL

205419 (MENB REC 2ND GEN-045 (V72_79))

Statistical Analysis Plan Amendment 3

SAP Version	Approval Date	Protocol Version (Date) on which SAP is Based	Change	Rationale
				
 Section 6.1 change in the strains testing strategy to have all strains tested
SAP Amendment 2	13 December 2022	Amendment 7: 11 October 2022	
 Section 2 updated primary safety endpoints to split assessment according to SFU period Section 3 change in study design graphical representation and definitions Table 3 extension of allowed visit window Section 5.5.1.2 change in Unsolicited AEs analysis 	
 In Protocol Amendment 7 the safety follow-up period has been shortened to 6 months in subjects who have not reached the 6-month safety follow-up after the last dose, at the time the amendment takes effect SFU changed Aims to mitigate the impact of COVID pandemic Endpoint update
SAP Amendment 3	03 Jun 2024	Amendment 7: 11 October 2022	
 Section 4 updated to remove unsolicited and solicited safety sets Table 5 updated 	
 Safety analyses will be conducted on the exposed set Alignment with current assay LOD, LLOQ and ULOQ values

CONFIDENTIAL

205419 (MENB REC 2ND GEN-045 (V72_79))

Statistical Analysis Plan Amendment 3

SAP Version	Approval Date	Protocol Version (Date) on which SAP is Based	Change	Rationale
			
• Section 5.5.1.1 updated to include analyses of Solicited AEs duration and onset day• Section 5.5.1.1 updated to track handling strategy for duplicate AEs• Section 5.5.1.2 added eDiary compliance analysis• Section 5.5.1.3 change to add definition and analysis of immediate unsolicited AEs• Section 8 added change in assay methodology• Section 10.1.3.11 updated Solicited AEs duration definition	
• Safety analyses update• Safety analysis clarification• Alignment with eCOA compliance expectations• Alignment with current expectations• Track change in assay methodology and impact on analyses• Alignment with current expectations

2. OBJECTIVES/ENDPOINTS

Objectives and endpoints are detailed in the table below:

Objectives	Endpoints
	Primary

To assess the safety and tolerability of rMenB+OMV NZ and MenACWY, when administered concomitantly or alone, in healthy subjects 16-18 years of age.
	
 • The frequencies and percentages of subjects with solicited local (i.e., injection site pain, erythema, swelling, induration) and systemic (i.e., fever [temperature $\geq 38.0^{\circ}\text{C}/100.4^{\circ}\text{F}$], nausea, fatigue, myalgia, arthralgia, headache) adverse events (AEs) during the 7 days (including the day of vaccination) following the first (Visit 1, Day 1/Month 0), the second (Visit 3, Month 2) and the third (Visit 4, Month 3) vaccination for all groups. • The frequencies and percentages of subjects with any unsolicited AEs (including all SAEs), AEs leading to withdrawal and medically attended AEs during the 30 days (including the day of vaccination) following the first (Visit 1, Day 1/Month 0), the second (Visit 3, Month 2) and the third (Visit 4, Month 3) vaccination for all groups. • The frequencies and percentages of subjects with SAEs, AEs leading to withdrawal, and medically attended AEs, throughout the study period (Day 1/Month 0 to Month 9). • The frequencies and percentages of subjects (who received rMenB+OMV NZ) with AESI throughout the study period (Day 1/Month 0 to Month 9). • Among subjects who are followed for 12 months after their last dose: 
 ○ The frequencies and percentages of subjects with SAEs, AEs leading to withdrawal, between SFU 5/Month 9 and SFU 7/Month 15 ○ The frequencies and percentages of subjects (who received rMenB+OMV NZ) with AESI between SFU 5/Month 9 and SFU 7/Month 15.

To demonstrate the non-inferiority of the antibody response to rMenB+OMV NZ given concomitantly with MenACWY to healthy subjects 16-18 years of age compared to rMenB+OMV NZ administered alone, as measured by serum bactericidal assay using human complement (hSBA) Geometric Mean Titers (GMTs) against N. meningitidis serogroup B indicator strains M14459 (fHbp), 96217 (NadA), NZ98/254 (PorA) and M07-0241084 (NHBA), at one month after the second vaccination with rMenB+OMV NZ.
 
Criterion: Non-inferiority will be demonstrated if for each of the four serogroup B test strains, the lower limit of the 2-sided 95% confidence interval of the between-group ratio of hSBA GMTs (rMenB+OMV NZ with MenACWY versus rMenB+OMV NZ alone) is >0.5.
	
Co-primary endpoints for Group MenB+MenACWY and Group MenB are the hSBA GMTs for rMenB+OMV NZ against each of the four serogroup B test strains (M14459, 96217, NZ98/254 and M07-0241084) at one month after the second vaccination with rMenB+OMV NZ (Visit 4, Month 3).

CONFIDENTIAL

205419 (MENB REC 2ND GEN-045 (V72_79))

Statistical Analysis Plan Amendment 3

Objectives	Endpoints

To demonstrate the non-inferiority of the antibody response to MenACWY given concomitantly with rMenB+OMV NZ to healthy subjects 16-18 years of age compared to MenACWY administered alone, as measured by hSBA GMTs against each of the N. meningitidis serogroups A, C, W and Y, at one month after the (study) vaccination with MenACWY.
 
Criterion: Non-inferiority will be demonstrated if for each of the four serogroups A, C, W and Y, the lower limit of the 2-sided 95% confidence interval of the between-group ratio of hSBA GMTs (rMenB+OMV NZ with MenACWY versus MenACWY alone) is >0.5.
	
Co-primary endpoints for Group MenB+MenACWY and Group MenACWY are the hSBA GMTs against each of the four serogroups A, C, W and Y with MenACWY at one month after the study vaccination of MenACWY (Visit 2, Month 1).

Secondary	

To assess the non-inferiority of the responses to MenACWY when given concomitantly with rMenB+OMV NZ to healthy subjects 16-18 years of age compared to MenACWY administered alone as measured by Enzyme-Linked Immunosorbent Assay (ELISA) Geometric Mean Concentration (GMCs) against each of the serogroups A, C, W and Y, at one month after the (study) vaccination with MenACWY.
 
Criterion: Non-inferiority will be demonstrated if for each of the four A, C, W and Y strains, the lower limit of the 2-sided 95% confidence interval of the between-group ratio of ELISA GMCs (MenACWY with rMenB+OMV NZ versus MenACWY alone) is >0.5.
	
Immune response to MenACWY The immune response to MenACWY when administered with/without rMenB+OMV NZ one month after the first vaccination (Visit 2, Month 1, Groups MenB+MenACWY and MenACWY) will be assessed for the serogroups A, C, W and Y as ELISA GMCs.

To assess the immune response to rMenB+OMV NZ in healthy subjects 16-18 years of age against N. meningitidis serogroup B test strains M14459 (fHbp), 96217 (NadA), NZ98/254 (PorA) and M07-0241084 (NHBA), at one month after the first and the second vaccination with rMenB+OMV NZ.
	
Immune response to rMenB+OMV NZ The immune response to rMenB+OMV NZ when administered with/without MenACWY will be evaluated by measuring bactericidal activity against N. meningitidis serogroup B test strains M14459, 96217, NZ98/254 and M07-0241084 in both MenB+MenACWY and MenB Groups as following:
 
 • GMTs at one month after first (Visit 2, Month 1) and second (Visit 4, Month 3) vaccination with rMenB+OMV NZ and Geometric Mean Ratio (GMRs) at one month after the first and the second rMenB+OMV NZ vaccination compared to the baseline at Visit 1, Day 1/Month 0. • The percentage of subjects with hSBA titers \geq Lower Limit of Quantitation (LLOQ) for each and all serogroup B test strains, one month after the first (Visit 2, Month 1) and second (Visit 4, Month 3) vaccination. • The percentage of subjects with fourfold increase in hSBA titers relative to baseline (Visit 1, Day 1/Month 0) defined as: 
 – For a pre-vaccination titer < limit of detection (LOD), a post-vaccination titer (Visit 2, Month 1 and Visit 4, Month 3) of \geq fourfold the LOD or \geq LLOQ, whichever is greater,

CONFIDENTIAL

205419 (MENB REC 2ND GEN-045 (V72_79))

[figure not shown]
Statistical Analysis Plan Amendment 3

Objectives	Endpoints

To assess the immune response to MenACWY in healthy subjects 16-18 years of age against each of the serogroups A, C, W and Y, at one month after the (study) vaccination with MenACWY.
	
 – For a pre-vaccination titer \geq LOD but $<$ LLOQ, a post vaccination titer (Visit 2, Month 1 and Visit 4, Month 3) of at least fourfold the LLOQ, – For a pre-vaccination titer \geq LLOQ, a post vaccination titer (Visit 2, Month 1 and Visit 4, Month 3) of at least fourfold the pre-vaccination titer (for Groups MenB+MenACWY and MenB). • The ratio of GMTs (rMenB+OMV NZ when administered with MenACWY [Group MenB+MenACWY] versus rMenB+OMV NZ when administered alone [Group MenB]), one month after the first vaccination (Visit 2, Month 1). 
Immune response to MenACWY
 
The immune response to MenACWY when administered with/without rMenB+OMV NZ at baseline (i.e. pre-vaccination, Visit 1, Day 1/Month 0) and at one month after the first vaccination (Visit 2, Month 1; Groups MenB+MenACWY and MenACWY) will be assessed for the serogroups A, C, W and Y as:
 
 • The percentage of subjects with hSBA titers \geq LLOQ, for each serogroup. • GMRs at one month after first vaccination compared to baseline • The percentage of subjects with fourfold increase in hSBA titers relative to baseline (Visit 1, Day 1/Month 0) is defined as: 
 – For a pre-vaccination titer $<$ LOD, a post-vaccination titer (Visit 2, Month 1) of \geq fourfold the LOD or \geq LLOQ, whichever is greater, – For a pre-vaccination titer \geq LOD but $<$ LLOQ, a post vaccination titer (Visit 2, Month 1) of at least fourfold the LLOQ, – For a pre-vaccination titer \geq LLOQ, a post vaccination titer (Visit 2, Month 1) of at least fourfold the pre-vaccination titer (for Groups MenB+MenACWY and MenACWY).

CCI

*The NHBA indicator strain M07-0241084 may be subject to change during the study, before clinical testing starts.
In this case, this change will be documented in the clinical report.

3. STUDY DESIGN

Protocol waivers or exemptions are not allowed unless necessary for the management of immediate safety concerns. Therefore, adherence to the study design requirements, are essential and required for study conduct.

Approximately 945 subjects will be screened to achieve 750 evaluable subjects for an estimated total of 250 evaluable subjects per treatment group. Withdrawals will not be replaced.

- Type of study: self-contained
- Experimental design: Phase IIIB, observer-blind, randomised, controlled, multi-centric, study with 3 parallel groups.
- Duration of the study:
 - Epoch 001: Primary starting at Visit 1 (Day 1) and ending at Visit 4 (Day 91)
 - Epoch 002: Safety follow-up period starting at Visit 4 (Day 91) and ending at Study termination-call (Day 451 [Month 15] or Day 271 [Month 9] for subjects who have not reached Day 271 at the time Protocol Amendment 7 takes effect)
- Primary Completion Date (PCD): Study termination-call (Day 451 [Month 15] or Day 271 [Month 9] for subjects who have not reached Day 271 at the time Protocol Amendment 7 takes effect)
- End of Study (EoS): Last subject last visit (LSLV) [last concluding contact on Day 451 (Month 15) or Day 271 (Month 9) for subjects who have not reached Day 271 at the time Protocol Amendment 7 takes effect] or Date of the last testing/reading released of the Human Biological Samples or imaging data, related to primary and

CONFIDENTIAL

205419 (MENB REC 2ND GEN-045 (V72_79))

Statistical Analysis Plan Amendment 3

secondary endpoints, whichever occurs later. EoS must be achieved no later than 8 months after LSLV. EoS cannot be before LSLV.

- Study groups:
 - Group MenB+MenACWY: rMenB+OMV NZ given concomitantly with MenACWY at study Day 1; rMenB+OMV NZ at study Day 61; Placebo at study Day 91.
 - Group MenB: rMenB+OMV NZ given concomitantly with Placebo at study Day 1 and rMenB+OMV NZ at study Day 61; MenACWY at study Day 91.
 - Group MenACWY: MenACWY given concomitantly with Placebo at study Day 1; rMenB+OMV NZ at study Day 61 and at study Day 91.

Table 1 Study groups, treatment and epochs foreseen in the study

Study Groups	Number of subjects	Age (Min-Max)	Treatment name	Vaccine/Product name	Epochs (Blinding)	
					Epoch 001 (observer-blind)	Epoch 002 (observer-blind)
MenB+MenACWY	315	16 years – 18 years	Bexsero	rMenB+OMV NZ	x	x
			Menveo	MenACWY (MenA lyo+MenCWY liquid		
			Placebo	NaCl		
MenB	315	16 years – 18 years	Bexsero	rMenB+OMV NZ	x	x
			Menveo	MenACWY (MenA lyo+MenCWY liquid		
			Placebo	NaCl		
MenACWY	315	16 years – 18 years	Bexsero	rMenB+OMV NZ	x	x
			Menveo	MenACWY (MenA lyo+MenCWY liquid		
			Placebo	NaCl		

Table 2 Overview of study design: Vaccination and Blood Draw Schedule

Visits Study Day	Visit 1 Day 1	Visit 2 Day 31	Visit 3 Day 61	Visit 4 Day 91
Group MenB+MenACWY N=315	Blood Draw rMenB+OMV NZ MenACWY			Blood Draw Placebo
Group MenB N=315	Blood Draw rMenB+OMV NZ Placebo	Blood Draw	rMenB+OMV NZ	Blood Draw MenACWY
Group MenACWY N=315	Blood Draw MenACWY Placebo			Blood Draw rMenB+OMV NZ

- Control: active control.
- Vaccination schedules: Day 1 (Visit 1), Day 61 (Visit 3) and Day 91 (Visit 4)
- Treatment allocation: Subjects to be randomised in a 1:1:1 ratio at Visit 1 (Day 1) to Groups MenB+MenACWY, MenB and MenACWY.
- Blinding: observer-blind.
- Sampling schedule:
 - Blood sampling: For all the 3 groups (i.e., Group MenB+MenACWY, Group MenB, and Group MenACWY), approximately 20 mL sample of blood will be drawn at Visit 1 (Day 1) before the first vaccination, at Visit 2 (Day 31) and at Visit 4 before vaccination (Day 91).
 - Urine sampling: Urine samples for pregnancy testing will be collected from female subjects at Visit 1, Visit 3 and Visit 4 prior to the vaccinations.

Data collection: Electronic Case Report Form (eCRF). Solicited symptoms will be collected using a subject Diary (electronic Diary [eDiary]).

Whenever possible, the investigator should arrange study visits within the intervals described in the below table.

Table 3 Visit interval

Interval	Length of interval	Allowed interval
Visit 1 → Visit 2	30 days	23 - 58 days
Visit 1 → Visit 3	60 days	53 - 88 days
Visit 3 → Visit 4	30 days	23 - 58 days
Visit 4 → Visit 5	30 days	23 - 58 days

4. ANALYSIS SETS

4.1. Enrolled Set

All subjects who signed informed consent.

4.2. Exposed Set

All subjects that received at least one dose of the study treatment. The allocation to a group is done in function of the administered treatment.

4.3. Full Analysis Set

All subjects who received at least one dose of the study treatment and have post-vaccination immunogenicity data.

4.4. Per Protocol Set

All subjects who received at least one dose of the study treatment to which they are randomised and have post-vaccination data (Full Analysis Set) minus subjects with protocol deviations that lead to exclusion. PDs leading to a Per Protocol Set exclusion are detailed in Section 4.5.2.

4.5. Criteria for eliminating data from Analysis Sets

Elimination codes are used to identify subjects to be eliminated from analysis. Detail is provided below for each set.

4.5.1. Elimination from Exposed Set (ES)

Code 1030 (Study vaccine not administered at all), 800 (Fraudulent data) and code 900 (invalid informed consent or fraudulent data) will be used for identifying subjects eliminated from ES.

4.5.2. Elimination from Per-protocol analysis Set (PPS) and Full Analysis Set (FAS)

4.5.2.1. Excluded subjects

A subject will be excluded from the analysis under the following conditions

Table 4 Exclusion codes

Code	Condition under which the code is used	Visit (timepoints) where the code is applicable	Applicable for analysis set/endpoint
800	Fraudulent data	All	All
900	Invalid informed consent	All	All
1030	Study vaccine not administered at all	Visits 1, 3 and 4	All
1040	Administration of concomitant vaccine(s) forbidden in the protocol	Visit 1, 2 (before BS at M1)	PPS M1 and M3
1040	Administration of concomitant vaccine(s) forbidden in the protocol	Visit 2 (after BS at M1), 3, 4 (before BS at M3)	PPS M3
1050	Randomisation failure	Visit 1	PPS M1 and M3
1060	Randomisation code was broken	All	PPS M1 and M3
1070	Subjects got vaccinated with the correct vaccine but containing a lower volume	Visit 1	PPS M1

CONFIDENTIAL

205419 (MENB REC 2ND GEN-045 (V72_79))

Statistical Analysis Plan Amendment 3

Code	Condition under which the code is used	Visit (timepoints) where the code is applicable	Applicable for analysis set/endpoint
1070	Subjects got vaccinated with the correct vaccine but containing a lower volume	Visit 3	PPS M3
1070	Vaccination not according to protocol	Visit 1	PPS M1
1070	Vaccination not according to protocol	Visit 3	PPS M3
1080	Vaccine temperature deviation	Visit 1	PPS M1
1080	Vaccine temperature deviation	Visit 3	PPS M3
1090	Expired vaccine administered	Visit 1	PPS M1
1090	Expired vaccine administered	Visit 3	PPS M3
2010	Protocol violation (inclusion/exclusion criteria)	All	PPS M1 and M3
2040	Administration of any medication forbidden by the protocol	Visit 1, 2 (before BS at M1)	PPS M1 and M3
2040	Administration of any medication forbidden by the protocol	Visit 2 (after BS at M1), 3, 4 (before BS at M3)	PPS M3
2050	Not withdrawn after developing withdrawal criteria other than prohibited concomitant vaccination/medication (medical condition forbidden)	All	PPS M1 and M3
2060	Concomitant infection related to the vaccine which may influence immune response (only meningococcal infection)	All	PPS M1 and M3
2080	Subjects did not comply with vaccination schedule	Visit 1	PPS M1
2080	Subjects did not comply with vaccination schedule	Visit 3	PPS M3
2090	Subjects did not comply with blood sample schedule	Visit 2	PPS M1
2090	Subjects did not comply with blood sample schedule	Visit 4	PPS M3
2100	Serological results not available post-vaccination for any of the four N. meningitidis serogroup B indicator strains	Visit 2	FAS and PPS M1 (secondary objective)
2100	Serological results not available post-vaccination for any of the four N. meningitidis serogroup B indicator strains	Visit 4	FAS and PPS M3 (primary objective)

CONFIDENTIAL

205419 (MENB REC 2ND GEN-045 (V72_79))

Statistical Analysis Plan Amendment 3

Code	Condition under which the code is used	Visit (timepoints) where the code is applicable	Applicable for analysis set/endpoint
2100	Serological results not available post-vaccination for any of the N. meningitidis serogroups A, C, W and Y (hSBA)	Visit 2	FAS and PPS M1 (primary objective)
2100	Serological results not available post-vaccination for any of the N. meningitidis serogroups A, C, W and Y (ELISA)	Visit 2	FAS and PPS M1 (secondary objective)
2120	Obvious incoherence or abnormality or error in data for any of the four N. meningitidis serogroup B indicator strains	Visit 2	FAS and PPS M1 (secondary objective)
2120	Obvious incoherence or abnormality or error in data for any of the four N. meningitidis serogroup B indicator strains	Visit 4	FAS and PPS M3 (primary endpoint)
2120	Obvious incoherence or abnormality or error in data for any of the N. meningitidis serogroups A, C, W and Y (hSBA)	Visit 2	FAS and PPS M1 (primary endpoint)
2120	Obvious incoherence or abnormality or error in data for any of the N. meningitidis serogroups A, C, W and Y (ELISA)	Visit 2	FAS and PPS M1 (secondary objective)
2130	Subject bled despite it was not planned to be bled	All	PPS M1 and M3
2170	Pregnancy	Visit 1	PPS M1 and M3
2170	Pregnancy	Visit 3	PPS M3

M1 and M3: months of the study schedule at which the subject will be eliminated from a specific population, i.e., Day 31 and Day 91.

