5.4. Immunogenicity

5.4.1. Analysis of immunogenicity planned in the protocol

5.4.1.1. Primary endpoints

The primary analysis will be conducted using the PPS for the primary (non-inferiority) objective. If, in any study group, the percentage of enrolled or vaccinated subjects with serological results excluded from the per-protocol set for analysis of immunogenicity is 5% or more, a second analysis based on the Full Analysis Set (FAS) will be performed to complement the per-protocol analysis. Supportive analyses using the FAS will also be performed for the primary immunogenicity endpoints.

Within group assessment

- For Group MenB+MenACWY and Group MenB: hSBA GMTs for rMenB+OMV NZ against each of the four serogroup B test strains (M14459, 96217, NZ98/254 and M07-0241084) at one month after the second vaccination for rMenB+OMV NZ (Visit 4) will be calculated.
- For Group MenB+MenACWY and Group MenACWY: hSBA GMTs against each of the four serogroups A, C, W and Y for MenACWY at one month after the study vaccination of MenACWY (Visit 2) will be calculated.

Between group assessment

- The ratio of GMTs between Group MenB+MenACWY versus Group MenB when administered without MenACWY [Group MenB]), at one month after the second vaccination will be calculated.
- The ratio of GMTs between Group MenB+MenACWY versus Group MenACWY when administered alone [Group MenACWY], at one month after the study vaccination of MenACWY will be calculated.

Primary immunogenicity endpoints may be repeated using another panel of strains, if requested.

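### Code 1060 in SAP Table 4 has no timing limit, so a code break after a blood sample removes the titre already drawn from the primary per-protocol set

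*SAP*

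**What the plan says.** The PPS carries the primary claim. SAP Section 5.4.1.1 states: "The primary analysis will be conducted using the PPS for the primary (non-inferiority) objective". The MenACWY co-primary endpoint is hSBA at Visit 2 (Month 1), and the MenB co-primary endpoint is hSBA at Visit 4 (Month 3), as set out in SAP Section 2.

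Table 4 in SAP Section 4.5.2.1 lists the exclusion codes with the visits and sets to which each applies. The footnote defines M1 and M3 as the "months of the study schedule at which the subject will be eliminated from a specific population, i.e., Day 31 and Day 91". Three kinds of row matter here:

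- **Code 1060**, "Randomisation code was broken", has All as its visit scope and removes both PPS M1 and PPS M3. It has no split before and after the sample.
- **Codes 1040 and 2040** (forbidden vaccine, forbidden medication) are each split at the sample. The row scoped "Visit 1, 2 (before BS at M1") removes M1 and M3. The row scoped "Visit 2 (after BS at M1), 3, 4 (before BS at M3") removes M3 only. No row covers an event after the M3 sample.
- **Codes 2050 and 2060** have the same scope as 1060. Code 2050 is worded "Not withdrawn after developing withdrawal criteria other than prohibited concomitant vaccination/medication (medical condition forbidden"), and code 2060 "Concomitant infection related to the vaccine which may influence immune response (only meningococcal infection").

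Code 2170 (pregnancy) is also visit-specific: Visit 1 removes both months and Visit 3 removes M3 only. None of codes 1060, 2050 and 2060 is listed as applying to the FAS.

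**The concern.** A per-protocol exclusion is justified when the deviation could have distorted the measurement. A code break after the sample does not meet that test. The serum is already in the tube, and Protocol Section 7.3 keeps the laboratory blind to treatment and subject number, with a different subject code at each timepoint. The rule therefore takes a valid titre out of the primary set because of something that happened later.

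That later event is also post-randomisation and may be related to what the subject received. Protocol Section 7.3.1 allows emergency unblinding, and allows safety staff to unblind for suspected unexpected serious reactions and for fatal or life-threatening cases, with no time limit. At stake is a small, avoidable selection step in the primary non-inferiority set. The SAP gives no reason for treating code 1060 differently from codes 1040 and 2040.

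**Working it through.** **Step 1. Compare the rows by timing of the event.** Entries show what leaves the PPS.

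| Event occurs | Codes 1040, 2040 | Code 1060 (also 2050, 2060) |
|---|---|---|
| Before the M1 sample | M1 and M3 | M1 and M3 |
| Between the M1 and M3 samples | M3 only | M1 and M3 |
| After the M3 sample | Nothing | M1 and M3, if the scope extends past Visit 4 |

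The middle row does not depend on how the all-visit scope is read. Even if it means only Visits 1 to 4, a break at Visit 3 (Day 61) removes an M1 titre drawn about 30 days earlier. The last row does depend on the reading. Contacts continue after the M3 sample: Visit 5 on Day 121 (Protocol Section 8.4.2) and safety calls to Day 271 or Day 451 (Protocol Section 8.4.3). No text excludes them from the scope, and none states that they are included.

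**Step 2. Reproduce the plan's power.** Inputs are from Protocol Section 10.1: margin 0.5, assumed ratio 0.9, the Est_sd column of Table 19, two-sided 95% CI, 250 evaluable per group.

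- Distance to the margin: log10(0.9) − log10(0.5) = 0.2553.
- For each test, the noncentrality is 0.2553 / (SD × √(2/n)), with power from the noncentral t on 2n − 2 degrees of freedom at one-sided 0.025.
- Example, M14459 at n = 250: 0.2553 / (0.72443 × √(2/250)) = 3.94, giving power 97.57%, as in Table 20.
- Multiplying the individual powers as the protocol does: hypothesis 1, 96.81%; hypothesis 2, 98.47%; hypothesis 3, 94.65%.
- All 12 tests: 0.9681 × 0.9847 × 0.9465 = 90.23%, matching Table 23. The 8 co-primary tests alone: 0.9681 × 0.9847 = 95.33%.

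**Step 3. Size a loss from the PPS.** One subject is 1/250 = 0.4% of a group. The documents give no rate for code breaks, so the losses below are assumptions, with n rounded down.

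| Assumed extra loss | n per group | Co-primary power | Power, all 12 tests |
|---|---|---|---|
| 0% | 250 | 95.33% | 90.23% |
| 1% | 247 | 95.01% | 89.65% |
| 2% | 245 | 94.79% | 89.25% |
| 5% | 237 | 93.79% | 87.47% |

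A 1% to 2% loss costs 0.3 to 0.5 points of co-primary power. Power is not the issue.

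**Step 4. Size code 2060.** Protocol Section 3.2 gives general-population incidences of invasive meningococcal disease: 0.18 per 100,000 in the US and 0.11 to 1.77 in European countries. Taking these as annual rates, with 945 subjects followed for 15 months (1.25 years):

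- Low: 945 × 0.11/100,000 × 1.25 = 0.0013 cases.
- US: 945 × 0.18/100,000 × 1.25 = 0.0021 cases.
- High: 945 × 1.77/100,000 × 1.25 = 0.021 cases.

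That is about 0.001 to 0.02 cases in the whole study. The rates are not specific to ages 16 to 18.

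**The case against.** The strongest reply is that this matters little in practice, and much of it stands.

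- **The data are not lost.** The codes act on the PPS only. SAP Section 5.4.1.1 plans a supportive FAS analysis of the primary endpoints regardless of the 5% trigger, and that analysis keeps these titres. This stands, although the PPS still decides the claim.
- **Code 2050 is narrow.** It needs a withdrawal criterion to be met and the subject not to be withdrawn. A reader might infer that any forbidden condition arising at, say, Month 6 costs both titres. The row does not say that. Protocol Section 7.7 treats such conditions as bars to further vaccination, and no dose is scheduled after Visit 4, so such a case may not trigger the code.
- **Code 2060 partly limits itself.** It covers only meningococcal infection that may influence the response, and the expected number is near zero.
- **Late events depend on reading the scope widely.** The numbered entries in that column run from Visit 1 to Visit 4, and contacts after Day 121 are calls rather than visits. A reader might infer that most triggering events fall after the Month 3 sample. That needs the wide reading and a roughly constant event rate, and the documents supply neither.
- **Dependence on arm is possible, not shown.** By the end of Visit 4 every group is scheduled to have had two rMenB+OMV NZ doses and one MenACWY dose, so a much later code break should depend little on arm. Against that, the Visit 4 injection itself differs by arm (placebo, MenACWY or rMenB+OMV NZ). Table 4 does not say whether sponsor safety unblinding triggers code 1060.

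None of this removes the central point: a code break between the two samples takes out a Month 1 titre that it could not have affected.

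**Conclusion.** The point holds for code 1060 as a stated rule, not as missing detail. A break after the Visit 2 sample removes the Month 1 MenACWY co-primary titre from the primary set on any reading of the scope. Removal of the Month 3 MenB titre by a break after the Visit 4 sample rests on the scope including Visit 5 and later contacts. Codes 2050 and 2060 share the untimed scope but add little.

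The likely effect is small. No code-break rate is given, so the number affected cannot be estimated. A reader might infer that the non-inferiority result is biased in a known direction. The documents do not support that: they give no event rates by arm and no link between such events and titre. This is an optional but worthwhile correction to the definition of the primary set.

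**What to change.** Before unblinding, amend the Table 4 row for code 1060, and those for 2050 and 2060 for consistency, to the timing already used for 1040 and 2040:

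- event before the M1 sample: exclude from PPS M1 and M3;
- event between the M1 and M3 samples: exclude from PPS M3 only;
- event after the M3 sample: no exclusion.

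The cost is the wording of three table rows. No new data are needed, and the stated sample size and power do not change.
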